- "Reasonable Possibility", for the purposes of safety reporting, means there is evidence to suggest a causal relationship between the drug and the adverse event. Examples of evidence that would suggest a causal relationship between the drug and the adverse event are:
- A single occurrence of an event that is uncommon and known to be strongly associated with drug exposure.
- One or more occurrences of an event that is not commonly associated with drug exposure, but is otherwise uncommon in the population exposed to the drug. If the event occurs in association with other factors strongly suggesting causation (eg, strong temporal association, event recurs on rechallenge), a single case may be sufficiently persuasive; but often, more than one occurrence would be needed before the sponsor could make a determination of whether the drug caused the event.

Unexpected

An "unexpected" AE is an AE that is not listed in the Investigator Brochure or is not listed at the specificity or severity that has been observed. "Unexpected" also refers to AEs that are mentioned in the Investigator Brochure as occurring with a class of drugs or as anticipated from the pharmacological properties of the drug, but are not specifically mentioned as occurring with the study drug under investigation.

DOCUMENTING AND REPORTING OF ADVERSE OR SERIOUS ADVERSE EVENTS AND UNANTICIPATED PROBLEMS

The Sponsor-investigator is responsible for ensuring that AEs, SAEs, and UPs that are observed or reported during the study, as outlined in the prior sections, are recorded on the study adverse event log

Version 8.0 29

with AE collection timelines adhering to the standards of the Institution. All SAEs also must be reported according to the local IRB guidelines as well as to the CTI PVG

Adverse Event and Unanticipated Problem Reporting Period

The AE and UP reporting period for this study begins after first dose of study drug administration until 30 days after discontinuation of the study drug. Grade 3 or greater AEs, SAEs, or UPs that are encountered during the protocol specified AE reporting period should be collected, and followed to resolution or until the patient is lost to follow up or withdrawals consent. Resolution/stable means the subject has returned to baseline state of health or the Investigator does not expect any further improvement or worsening of the event.

Assessment of Adverse Events and Unanticipated Problems

Investigators will assess the occurrence of AEs, SAEs, and UPs at all patient evaluation time points during the study. Grade 3 or greater AEs, SAEs, and UPs whether volunteered by the patient, discovered by study personnel during questioning, or detected through physical examination, clinically significant laboratory test, or other means will be recorded in the patient's adverse event log.

Each recorded AE, SAE, or UP will be described by its duration (ie, start and end dates), severity, regulatory seriousness criteria, if applicable, suspected relationship to the investigational product (see following guidance), and any actions taken.

All deaths should be reported with the primary cause of death as the AE term, as death is typically the outcome of the event, not the event itself. The primary cause of death on the autopsy report (if done) should be the term reported.

An SAE will qualify for expedited reporting to regulatory authorities if the SAE is considered a Suspected Adverse Reaction and is not listed in the current Investigator's Brochure (ie, an unexpected event). To ensure consistency of AE and SAE causality assessments, investigators should apply the following general guideline:

Related to study drug: Any AE or UP (serious or not) that appears to have a reasonable possibility of causal relationship to the use of the study drug. Guidelines to determine whether an event might be considered related include (but are not limited to) the following:

- The event occurred in close temporal relationship to study drug administration.
- The event abated (diminished) or disappeared when treatment with the study drug was down-titrated, interrupted, or discontinued.
- The event re-occurred when treatment was re-introduced.

Unrelated to study drug: Any AE or UP (serious or not) that does not appear to have a reasonable relationship to the use of study drug.

Procedures for Reporting Drug Exposure During Pregnancy and Birth Events

Rules for contraception:

If fertile, both males and females must agree to use effective birth control. Women of childbearing potential must use highly effective methods (defined as those resulting in a failure rate of <1% per year when used consistently and correctly) for the duration of study treatment and for 12 months after last dose of study drug. The contraceptive methods considered highly effective are intrauterine devices and hormonal contraceptives (contraceptive pills, implants, transdermal patches, hormonal vaginal devices, or injections with prolonged release).

Version 8.0 30

Before study enrollment, subjects must agree to take appropriate measures to avoid pregnancy. Report any pregnancy that occurs in a patient or patient's partner from the time of consent to 365 days after the last dose of study drug. Record any occurrence of pregnancy in the patient's medical records and notify the treating physician within 24 hours of learning of the event. Abortion, whether therapeutic, elective or spontaneous, will be reported as an SAE.

A patient must immediately inform the investigator if the patient or patient's partner becomes pregnant from the time of consent to 365 days after the last dose of study drug. Any female patients receiving pacritinib PO who become pregnant must immediately discontinue the drug. The investigator should counsel the patient, discussing any risks of continuing the pregnancy and any possible effects on the fetus. Although pregnancy itself is not regarded as an AE, the outcome will need to be documented. Report any pregnancy that occurs in a subject or subject's partner from the time of consent to 365 days after the last dose of study drug. Record any occurrence of pregnancy on appropriate case report form and fax it to Cell Therapeutics, or designee, within 24 hours of learning of the event. The pregnant female will be followed for outcome, which is defined as elective termination of the pregnancy, miscarriage, or delivery of the fetus. For pregnancies with an outcome of live birth, the newborn infant will be followed until 30 days old by completing the Pregnancy Report Form Part II. Any congenital anomaly/birth defect noted in the infant must be reported as an SAE.

Expedited Reporting Requirements for Serious Adverse Events

Serious, unexpected, and suspected adverse events must be reported to FDA, local IRB, and Cell Therapeutics within 24 hours of the principal investigator's knowledge of the event. Such IND safety reports should be submitted in a narrative format or on FDA Form 3500A or in an electronic format that FDA can process, review and archive.

CTI Pharmacovigilance FAX #: [name] E-mail: [contact]

The study number should be referenced on the fax or subject line of the notification. Additional follow-up information should be completed on a SAE follow-up form as soon as it becomes available and should cross reference the initial SAE report form.

Routine Adverse Event Reporting

Adverse events which are not serious, unexpected and suspected do not require expedited reporting, but rather will be submitted per local IRB standards on an annual basis or more frequently as required.

Type and Duration of Follow-up of Patients after Adverse Events

AEs and SAEs that are encountered during the protocol-specified AE reporting period should be followed to resolution, or until the investigator assesses the patient as stable, or the patient is lost to follow-up or withdraws consent.

4. Suspension/Termination

The PMC and/or the IRB may vote to suspend or terminate approval of a research study not being conducted in accordance with the IRB, the Cancer Center and/or regulatory requirements or that has been associated with unexpected problems or serious harm to subjects. The PMC/IRB will notify the PI in writing of such suspension or terminations. It is the responsibility of the PMC/IRB Chairperson to ensure prompt written notification of

any suspensions or terminations of PMC/IRB approval to the relevant Federal Agencies, including OHRP, FDA, and if applicable, the Affiliate Program.

5. Trial Discontinuation

For reasonable cause the Investigator and/or Moffitt Cancer Center may terminate this study prematurely. Conditions that may warrant termination include, but are not limited to: the discovery of an unexpected, significant, or unacceptable risk to the patients enrolled in the study or if the accrual goals are met. A written notification of termination will be issued.

External study site compliance

Compliance to the Protocol and Adherence to Moffitt External Site Coordination Handbook

Moffitt is responsible for monitoring each sites compliance to adherence to applicable Moffitt External Site Coordination Handbook. In coordination with the Monitoring office, the ESC Office assists to monitor compliance to the protocol.

External Site Access to Clinical Trial Database

To obtain access to OnCore, the External Site Coordinator will supply forms required to be completed by the site staff. Once the completed forms are received, the site coordinator will receive VPN access, logon/password, and information on how to access OnCore. The ESC office will provide OnCore training to the site once initial access is granted and on an ongoing basis, as needed.

Registration Procedures for External Sites

All external enrolled subjects must be registered with the External Site Coordination (ESC) office to be able to participate in a trial. The participating site must email the completed current eligibility checklist, registration form, all supporting documents, and signed, unredacted informed consent to the Coordinating Center. Unsigned or incomplete forms will be returned to the site. Once documents are received, the ESC Coordinator will review them to confirm eligibility and complete the registration process. If eligibility cannot be confirmed, the research coordinator will query the site for clarification or additional documents as needed. Subjects failing to meet all study eligibility requirements will not be registered and will be unable to participate in the trial.

Upon completion of registration, the ESC Coordinator will provide the participating site with the study sequence number and, when applicable, randomization information. Within 48 hours after registration, it is the site's responsibility to:

Enter the on-study patient information into the Oncore database

Version 8.0 32

Order investigational agent(s) if indicated per protocol

It is the responsibility of the participating Investigator or designee to inform the subject of the research treatment plan and to conduct the study in compliance with the protocol as agreed upon with Moffitt Cancer Center and approved by the site's IRB.

To register a patient, send the completed signed eligibility checklist along with the patient registration form and supporting documentation to the ESC via email at [contact], Monday through Friday between 8:00AM and 5:00PM (EST). If a short turnaround time is required between registration and first treatment, please consider discussing this with you ESC Coordinator and, if possible, submit a partial submission.

Required Documentation for External Sites

Before the study can be initiated at any site, the site will be required to provide regulatory documentation to the External Site Coordination (ESC) office at Moffitt Cancer Center. Sites must provide a copy of their informed consent to the ESC office for review and approval prior to submission of any documents to the site's IRB. Any changes requested by the site's IRB must be provided to the ESC staff for review and approval prior to resubmission to the IRB.

The ESC office must receive the following trial specific documents either by hardcopy or email before a site can be activated for any trial. All corresponding updates to these documents are required to be submitted to the ESC office throughout the trial:

- IRB Approval Letter that includes the protocol version and date
- FDA Form 1572 Protocol Signature Page
- Investigator Brochure (or Package Insert) Signature Page(s)
- IRB Approved Consent Form
- Site Delegation of Authority Log
- Signed Financial Interest Disclosure Forms (For all individuals listed on the 1572)
- Investigator/Personnel documents (CVs, licenses, GCP and HSP training certificates, etc.) as needed
- Laboratory Documents (certifications, normal ranges, etc.) as needed
- Signed Clinical Trial Agreement
- Protocol specific documentation as needed

Version 8.0 33

A study initiation teleconference will be held prior to the start of any study related activity at the site. Attendance is required for:

The site PI and appropriate research staff

Moffitt PI and ESC Coordinator

The requirements of the protocol and all associated procedures and processes will be reviewed and agreed upon prior to the activation of the study. The ESC utilizes the EDC system, OnCore training will be scheduled, if indicated, with the appropriate staff from the site.

External sites are required to send updated documentation to the ESC Office at [contact] within 10 business days of updating.

SAE Reporting Special Language for External Sites

Information about all serious adverse events will be collected and recorded. To ensure patient safety, each serious adverse event must be reported to the PI and to the sponsor expeditiously. Moffitt Cancer Center and all participating sites will report SAEs by completing an SAE report in OnCore, the electronic data capture system. The SAE Report from OnCore must be signed and reported by email ([contact]) to the External Site Coordination (ESC) office within 2 working days. If applicable, the site should also follow protocol guidelines for additional reporting to Financial Sponsors and government agencies.

External Site Monitoring and Reporting

The Coordinating Center will implement ongoing monitoring activities to ensure that Participating Institutions are complying with regulatory and protocol requirements, data quality, and participant safety. Monitoring practices may include but are not limited to source data verification, and review and analysis of eligibility requirements, informed consent procedures, adverse events and all associated documentation, review of study drug administration/treatment, regulatory files, protocol departures reporting, pharmacy records, response assessments, and data management. All monitoring efforts will occur based on the protocol specific monitoring plan. Following each monitoring visit, a monitoring follow-up report will be provided to the Participating Site (i.e. Site PI and Coordinator). The monitoring report will summarize any issued queries or data clarification requests, identify any reportable events or required follow-up on prior events and will specify details of any non-compliance. Participating Sites are requested to respond to all queries and data clarifications requests within 20 business days. The Moffitt Cancer Center Protocol Monitoring Committee will review all monitoring reports and issue resolution. This Committee reserves the right to close accrual for non-compliance to monitoring.

VII. Ethics

This study will be conducted according to US and international standards of Good Clinical Practice (FDA Title 21 part 312 and International Conference on Harmonization guidelines, including parts 50 and 56 concerning informed consent and IRB regulations) applicable government regulations and Institutional research policies and procedures.

All subjects for this study will be provided a consent form describing this study and providing sufficient information for subjects to make an informed decision about their participation in this study. This consent form will be submitted with the protocol for review and approval by the IRB for the study. The formal consent of a subject, using the IRB-approved consent form, will be obtained before that subject undergoes any study procedure.

This protocol and any amendments will be submitted to a properly constituted Institutional Review Board (IRB), in agreement with local legal prescriptions, for formal approval of the study conduct. IRB approval will be secured prior to commencement of this study.

VIII. Publication policy

- a. The primary investigator is responsible for analyzing the data and drafting a manuscript for publication.
- b. Secondary investigators will offer critical review of this manuscript and therefore will be cited as secondary authors.

IX. Records Retention

U.S. FDA regulations (21 CFR §312.62[c]) require that records and documents pertaining to the conduct of this study and the distribution of investigational drug, including CRFs, consent forms, laboratory test results, and medication inventory records, must be retained by the Principal Investigator for 2 years after marketing application approval. If no application is filed, these records must be kept 2 years after the study is discontinued and the U.S. FDA and the applicable national and local health authorities, including the National Heart, Lung, and Blood Institute (NHLBI), are notified.

X. References:

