Trial Design: This is a single-arm, phase I/II, study of PAC/SIR/TAC for the prevention of acute GVHD after matched related and unrelated alloHCT. First, a standard 3+3 dose escalation method will be performed combining PAC with SIR/TAC. The MTD identified during phase I, as well as serial PK/PD data, will inform the recommended phase II dose. Therefore, the recommended phase II dose will be the lowest dose that decreases the amount of pSTAT3+ CD4+ T-cells <35% at day +21 and does not exceed the MTD (see Table 1). The phase II component is powered to determine if JAK2 inhibition with PAC significantly reduces CD4+ T-cell STAT3 activation early after allogeneic HCT compared to our historical benchmark. Our published study showed the mean CD4+ T-cell STAT3 phosphorylation at day +21 was 50% among all HCT recipients, 70% for those who later developed acute GVHD, versus 32% for those who did not². Therefore, success will be defined as a reduction in CD4+ T-cell STAT3 phosphorylation to 35% or less at day +21. This phosphorylation value not only estimates biologic activity, but also falls within the standard deviation of what was observed among HCT recipients who never acquired acute GVHD². The association of CD4+ T-cell STAT3 phosphorylation and acute GVHD risk is under prospective validation, but currently offers guidance in determining the degree of on-target pathway suppression for HCT recipients on this trial. As pacritinib is a direct inhibitor of JAK2/STAT3 signal transduction, greater reduction in CD4+ T-cell pSTAT3 phosphorylation is possible in this patient population. An initial 24 patients will be treated with PAC/SIR/TAC to investigate whether the biologic activity of STAT3 in CD4+ T-cells is reduced at day +21.

Secondarily, we will monitor enrolled patients for acute GVHD by day +100. To investigate the clinical efficacy of the PAC/SIR/TAC combination in GVHD prevention, the trial will be expanded by an additional 14 subjects if 9 or less of the first 24 patients develop grade II-IV acute GVHD. This expansion threshold is based on our data from the SIR/TAC trial where the cumulative incidence of acute GVHD incidence by day +100 was 43%. PAC/SIR/TAC will be considered favorable if the primary endpoint is met AND ≤12 of the total 38 (31.6%) patients develop acute GVHD by day +100.

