(Dose level 1) PAC 100mg po daily, (Dose level 2) PAC 100mg po twice daily, and (Dose level 3) PAC 200mg po twice daily. Dose cohort 1 (PAC 100mg daily) represents the lowest dose level that would potentially inhibit CD4+ T-cell pSTAT3. This is based on PK/PD data from the completed phase I trial of pacritinib in lymphoma⁷. For all patients enrolled in the phase I portion of this study, pharmacokinetic sampling of plasma pacritinib levels will be drawn on days 0 and +21 at the following time points: predose. +4 hours. +12 hours. and +24 hours (window of +/- 1 hour on each timed PK sample). Pharmacodynamic, CD4+ T-cell pSTAT3 values will be assessed at baseline and day +21 as well. EKGs (on days 0 and +21) will be performed pre-dose and at 4 hours (pacritinib Tmax)⁷ – with +/- 1 hour window on the 4-hour post-dose EKG. The initial group of 3 patients will be enrolled in cohort 1. Dose escalation of pacritinib will proceed according to the following: If no DLT is observed among 3 patients in a cohort AND the average %pSTAT3+ CD4+ T-cells are >35% at day +21, the next group of 3 will be treated at the next highest dose level. If the current level (i.e., the level at which no DLTs are observed) is the highest dose level, three additional patients will be enrolled (total of six). If one DLT is observed among 3 patients in a cohort, the next group of 3 will be treated at this same dose level. If no more DLT is observed among the 3 additional patients (i.e. one DLT in total is observed among the 6 patients) AND the average %pSTAT3+ CD4+ T-cells are >35% at day +21, then the next 3 patients will be treatment at the next highest dose level. If at least 1 more DLT is observed among the 3 additional patients, then the MTD is exceeded. If 6 patients have been treated at the next lower dose level, it will be considered as the MTD. If not, three additional patients will be enrolled. This escalation approach will then be continued until MTD or a tolerated dose (≤1/6 DLT) is identified at which <35% of the CD4+ T-cells are pSTAT3+.on day +21 (see Table 1). That dose will be considered to be the recommended phase II dose. The total number treated on the phase I component will depend on the occurrence of dose limiting toxicity (DLT) or the average frequency of pSTAT3+ CD4+ T-cells at day +21 in a cohort, however the maximal number accrued on the phase I study would approximate 12 to 18 total evaluable subjects. Patients in the phase I component of the trial will be monitored throughout their 100 days of pacritinib therapy for DLT events, however the minimum DLT observation period required prior to escalation to higher dose levels in the phase I component is 30 days from the last patient's (within dose level) initiation of pacritinib therapy. In addition to informing the recommended phase II dose, the PK/PD data from days 0 and +21 will be used to identify any dose-dependent patterns among serum pacritinib concentrations and 1) CD4+ T-cell STAT3 phosphorylation, 2) Treg reconstitution, 3) QTcF prolongation, or 4) changes in plasma tacrolimus and sirolimus levels.

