
Table 1: Phase I: Identification of Recommended Phase II Dose		
Dose Level	MTD exceeded	Day +21 pSTAT3+ CD4+ T-cells <35%
Dose cohort 1 (100 mg daily)	Yes (Stop, do not proceed)	Yes (treat a total of 6, RP2D identified if ≤1/6 have DLT)
	No (Proceed)	No (Proceed to cohort 2)
Dose cohort 2 (100 mg BID)	Yes (Stop, return to complete 6 subjects in cohort 1)	Yes (treat a total of 6, RP2D identified if ≤1/6 have DLT)
	No (Proceed)	No (Proceed to cohort 3)
Dose cohort 3 (200 mg BID)	Yes (Stop, return to complete 6 subjects in cohort 2)	
	No (RP2D identified, proceed to phase II component of trial))	

The definitions for DLTs on PAC/SIR/TAC are as follows (CTCAE v4):

- 1. Left ventricular systolic dysfunction grade 3 or above*
- 2. Myocardial infarction grade 3 or above
- 3. Atrial fibrillation or flutter grade 3 or above
- 4. Supraventricular tachycardia grade 3 or above
- 5. Ventricular arrhythmia grade 3 or above
- 6. Upper or lower gastrointestinal hemorrhage grade 3 or above
- 7. Intracranial hemorrhage grade 1 or above
- 8. Any grade 3 or above adverse event considered at least possibly related to pacritinib

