- 9. Grade 3 or higher recent (within the past 6 months) or ongoing bleeding events.

10. Symptomatic or uncontrolled cardiovascular disease, myocardial infarction or severe/unstable angina within the past 6 months, or New York Heart Association Class III or IV congestive heart failure

c. Donor eligibility

Eligible donors will include healthy sibling, relative or unrelated donors that are matched with the patient at HLA-A, B, C, and DRB1 by high resolution typing as defined by the Collaborative Trials Network²⁹.

V. Study Design

1. Sample size

a. A total of up to 12-18 evaluable patients will be enrolled in phase I. The 6 patients treated at the MTD (or lowest biologically active dose) in phase I will be analyzed among those treated in phase II. In phase II, 24 evaluable patients will be enrolled to study CD4+ T-cell STAT3 phosphorylation at the MTD. Additional 14 evaluable patients will be accrued to expansion stage if 9 or less of the initial patients treated at the MTD develop grade II-IV acute GVHD. Thus, a total of up to 50 evaluable patients could be enrolled to the combined phase I and II components of the trial. We anticipate up to 63 total could be enrolled and treated with PAC/SIR/TAC (which would account for a 10% replacement for non-evaluable subjects in phase II, and possible 10 subjects non-evaluable in the phase I component of the trial).

Withdrawal

- a. Subject withdrawal from the study will take place under the following circumstances:
 - i. those patients who sign consent for the study, but fail to initiate treatment on account of:
 - 1. denial of coverage from insurance provider
 - 2. death prior to initiation of treatment
 - 3. withdrawal of patient consent at any time after therapy

Subjects who withdraw consent for pacritinib therapy after day +21 but before day +100 will be asked to continue on study for follow-up of their condition and allow collection of research blood samples. These patients will be considered "off-therapy, on-study" reflecting **partial** withdrawal of consent. These patients will inform the secondary endpoint of GVHD prevention, and only be excluded from the analysis if they are off pacritinib for more than 4 weeks and do not resume the drug thereafter for causes other than acute GVHD (treatment failure). Subjects who withdraw consent for pacritinib therapy before day +21 will be excluded from any study analysis reflecting **full** withdrawal of consent.

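### Phase I can report a lowest biologically active dose that never met the protocol's own criterion of day +21 pSTAT3 below 35%

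*Combined protocol and SAP*

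**What the plan says.** **Definition and endpoint.** The Trial Design paragraph states that "the recommended phase II dose will be the lowest dose that decreases the amount of pSTAT3+ CD4+ T-cells <35% at day +21", adds that this dose must not exceed the MTD, and points to Table 1. Sections II and III make the lowest biologically active dose that is safe and tolerated the phase I primary objective and endpoint. The paragraph after the DLT list gives the same basis for the RP2D.

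**Escalation text (Protocol design paragraph).**
- The step up with no toxicity is conditioned as follows: "If no DLT is observed among 3 patients in a cohort AND the average %pSTAT3+ CD4+ T-cells are >35% at day +21".
- At the highest level with no DLT, "three additional patients will be enrolled (total of six"; no pSTAT3 condition is attached.
- Escalation is "continued until MTD or a tolerated dose (≤1/6 DLT) is identified at which <35% of the CD4+ T-cells are" pSTAT3-positive on day +21. The next sentence makes that dose the RP2D.
- If a level exceeds the MTD, the next lower level becomes the MTD once six patients have been treated there.

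**Table 1.**
- At levels 1 and 2, once the activity column is met: "Yes (treat a total of 6, RP2D identified if ≤1/6 have DLT".
- At level 3, in the column for the MTD: "No (RP2D identified, proceed to phase II component of trial".
- After toxicity at level 2 or 3, the instruction is to return and complete six patients at the level below.

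Section V.7 defines the MTD by at most one DLT in six, and says that safety and biologic activity together determine the RP2D.

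**The concern.** The definition has two conditions, activity and tolerability. The operating rules contain routes on which only tolerability is applied. Because the phase I primary endpoint is named after activity, following the plan to the letter could lead to a report that the endpoint was found when day +21 pSTAT3 at the chosen dose was 35% or more.

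There is also a gap at levels 1 and 2. If no DLT occurs, the average that stops escalation comes from three patients. Three more are then treated, and Table 1 names only their DLTs as the remaining condition. Nothing says what follows if the six-patient average is no longer below 35%.

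What is at stake is what phase I may be said to have shown. The choice of dose itself is not questioned here.

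**Working it through.** **1. The passages side by side**

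| Route to the RP2D | Tolerability required | pSTAT3 below 35% required |
|---|---|---|
| Trial Design definition | Yes | Yes |
| Table 1, levels 1 and 2 | Yes, on six | Yes, but three or six patients not stated |
| Table 1, level 3 | Yes | No |
| Protocol design, MTD as end-point | Yes | No |

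The level 3 reading rests on the wording in the MTD column. It would stand even if the blank activity cell were lost in reading the PDF.

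On the return route, level 2 is reached only after level 1 averaged above 35%, and level 3 only after level 2 did. A lower level completed to six after toxicity is therefore one that was first left for insufficient activity. No renewed activity check is stated.

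**2. Inputs and the plan's own figures**

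Section V.7 gives a historical day +21 mean of about 50 and SD of about 25 (n = 18), with SD 20 as the alternative. Its power figures reproduce with the noncentral t distribution:
- N = 24, effect 15/25 = 0.60: 80.4% (stated 80%)
- N = 24, effect 15/20 = 0.75: 94.0% (stated 94%)
- N = 38, effect 0.60: 95.0% (stated 95%)

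The documents give no operating characteristic for the phase I activity rule.

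**3. An inactive level (true mean 50), normal model**

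Standard error of a three-patient mean: 25/√3 = 14.4 points, about the size of the 15-point target.

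P(mean of 3 < 35) = Φ((35 − 50)/14.4) = Φ(−1.04) = 14.9%.

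With SD 20: 20/√3 = 11.5, and Φ(−1.30) = 9.7%.

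For six patients: 25/√6 = 10.2, and Φ(−1.47) = 7.1% (SD 20: 3.3%).

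The three-patient and six-patient means have correlation √(3/6) = 0.707. The bivariate normal probability that both are below 35 is 4.7% (SD 20: 2.1%).

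A bounded Beta(1.5, 1.5) model with the same mean and SD gives 15.6% and 4.8%.

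**4. How often a pass on three fails to hold on six (SD 25)**
- True mean 50: 1 − 0.0466/0.1493 = 69%
- True mean 40: 1 − 0.2225/0.3645 = 39%
- True mean 35: 1 − 0.375/0.5 = 25%

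**5. The whole of phase I, true mean 50 at every level, no DLTs**

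RP2D at level 1: 14.9%. At level 2: 0.851 × 0.149 = 12.7%. At level 3: 0.851² = 72.4%. The sum is 100%, so an RP2D is always declared.

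The six-patient mean at the declared dose is below 35% in 0.0466 + 0.851 × 0.0466 + 0.724 × 0.0708 = about 14% of runs.

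The documents give no DLT rate, so the following rates are assumptions. The simulation judges the average on six patients after one DLT in three, and leaves out the return route.

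| Assumed DLT rate | RP2D declared | Declared with six-patient mean < 35% |
|---|---|---|
| 10% | 76% | 12% |
| 20% | 39% | 7% |
| 30% | 15% | 4% |

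**The case against.** **The MTD is a written fallback.** The Protocol design paragraph names two end-points, and the level 3 row carries out the first. This stands: the rules can be followed, and it would be too strong to infer that the passages are irreconcilable. But the Trial Design definition omits the fallback, and the endpoint's name does not allow for it.

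**Levels 1 and 2 can be read as a six-patient condition.** The phrase "a tolerated dose (≤1/6 DLT) is identified at which <35% of the CD4+ T-cells are pSTAT3"-positive permits that reading, and after one DLT in three the average is considered again on six. A reader might infer that the last three patients' values are ignored. The documents do not say so, and Section V.7 requires a patient without a DLT to be on pacritinib near the day +21 sample to be evaluable. This part is a gap, not a contradiction.

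**The return route does not declare a dose in Table 1.** The table says only to complete six, and the added patients could bring the average below 35%. This stands. The route to the RP2D without activity comes from the Protocol design text.

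**Section V.1.** A reader might see a rival rule in "24 evaluable patients will be enrolled to study CD4+ T-cell STAT3 phosphorylation at the MTD". The sentence before it speaks of the MTD or the lowest biologically active dose, so the phrase is best taken as shorthand.

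**Reaching level 3.** With a true mean of 40% at levels 1 and 2 and SD 25, the chance of reaching level 3 is 0.6355² = 40% with no DLTs. A reader might take that as an error rate. It is not: such levels do not meet the criterion, so escalating follows the rule, and nothing is assumed about activity at level 3. The figure falls to 34%, 21% and 10% at assumed DLT rates of 10%, 20% and 30%.

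**Phase II tests pSTAT3 formally, and accrual is complete** (Section V.6, tissue-biopsy item). Both are true. They limit the consequence to what phase I may claim, and mean that any labelling rule now comes after dose selection.

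**Conclusion.** The point holds in a limited form. The definition of the RP2D requires day +21 pSTAT3 below 35%, while Table 1 at level 3 and the MTD end-point in the Protocol design text do not. Phase I can therefore report a lowest biologically active dose without its criterion being met.

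At levels 1 and 2 with no DLT, the number of patients on whom the average is judged is not settled. That ambiguity is worth roughly a factor of three or more in false passes for an inactive level: 14.9% against 4.7% at SD 25, and 9.7% against 2.1% at SD 20. These figures assume independent, roughly normal values around the plan's historical mean of 50. The bounded model changes them little. The whole-of-phase-I figures also assume the same mean at every level and DLT rates that the documents do not supply.

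**What to change.** 1. Reconcile the Trial Design paragraph, the Protocol design paragraph, the RP2D paragraph after the DLT list and Section V.7 with Table 1. Two questions need one answer each: whether the MTD alone can be the RP2D, and on how many patients the 35% average is judged. This review takes no position on which dose goes forward.
2. Report the day +21 pSTAT3 mean and confidence interval for all phase I patients at the selected dose who have a value, and give the number. A patient counted as evaluable because of a DLT may lack an on-drug value.
3. State whether the dose was selected on the activity criterion or as the MTD.
4. Use the label *lowest biologically active dose* only if that mean is below 35%. Otherwise report the phase I activity objective as not met.

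The cost is wording and one summary line, since day +21 pSTAT3 is already an assessment for phase I patients. There are two drawbacks. At a true mean of 35%, about a quarter of levels that pass on three patients would lose the label on six. And because accrual is complete, the rule must be disclosed as added after dose selection.
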